The following procedures will be taken to safeguard against adverse medication events: (1) careful initial intake evaluation to determine eligibility based on inclusion/exclusion criteria; (2) thorough physical evaluation prior to treatment, consisting of physical examination, standard laboratory tests, electrocardiogram, urine toxicology screen, pregnancy test and vital signs; (3) weekly review of treatment response, adverse events, concomitant medication use, and medication compliance; (4) regular evaluation by the study physician and Medical Director of the CNRA, [name] (**Co-I**).

Modafinil interacts with CYP3A4/5 and CYP2C19 substrates. At the initial intake evaluation, the study coordinator and/or nurse will screen potential subjects against the list of prohibited concomitant medications ("conmeds") including those metabolized by CYP3A4/5 (e.g., steroid contraceptives, cyclosporine, midazolam, triazolam, quetiapine) and CYP2C19 (e.g., phenytoin, diazepam, propranolol, omeprazole, clomipramine). Enrolled subjects will meet with the study nurse weekly during treatment to assess for any new medications. The Concomitant Medications Tracking Log will be used to record any medications taken during the study. The study nurse completing the form will enter the name of the medication, dose/unit, route of administration, date started/stopped, and indication. Reported use of prohibited conmeds will be reviewed by the study physician ([name], Co-I) who will make a reasonable judgement about continued participation in the study.

All participants will be monitored weekly during the study for treatment-emergent psychiatric symptoms. At each study visit monitoring procedures will include (1) The Systematic Assessment for Treatment and Emergent Events (SAFTEE), administered by trained research staff at each study visit to document patient-reported adverse events and/or treatment-emergent symptoms; (2) the Clinical Global Impression (CGI) scale, a well-established research rating tool for tracking clinical progress over study period and evaluating any change in the severity of psychopathology; (3) the Beck Depression Inventory-II, a 21-item, self-report rating inventory that measures symptoms of depression. Weekly individual therapy sessions conducted by trained licensed professional counselors under the supervision of a licensed clinical psychologist will provide additional monitoring of treatment-emergent psychiatric

symptoms. The study physician ([name], Co-I) will be alerted of any psychiatric adverse events or reactions of treatment such as suicidality or worsening of mood symptoms. If clinically indicated in cases of significant worsening or deterioration of patient's functioning, appropriate actions will be taken, including study termination with proper referral.

Modafinil is a schedule IV controlled substance. Our research pharmacy holds a current DEA Certificate of Registration (DEA Form 223) and complies with DEA Security Requirements regarding the storage of controlled substances in securely locked and substantially constructed cabinets. Inventory and recordkeeping requirements adhere to the DEA practitioner's manual. To prevent diversion, the pharmacists dispense one weeks' worth of study medications directly to the Research Nurse, who administers the medications directly to each study participant. Unused pills are returned by the patient to the study nurse at weekly scheduled clinic visits.

Confidentiality will be protected in several ways. All information collected solely for research purpose will be kept in locked, restricted access files. Subject records will be coded and filed by a number code. Subject identities will not be revealed in any publication of the data. Individual subject information will be transferred to outside sources only with the express written request of the subject. Subjects will receive a copy of their signed consent form.

Potential Benefits of the Proposed Research to the Subject and Others

All assessment and treatment services provided in this study will be at no cost to the subject. The treatments should help in stopping cocaine use and preventing relapse. Subjects will be told if unusual information is discovered during the study that will make a difference in treatment for this or other problems. By taking part in this research subjects will help others with similar problems because this study is likely to identify what types of treatment work best and for whom.

Importance of the Knowledge to be Gained

Research participation may assist subjects in abstaining from cocaine during treatment and beyond. Cocaine dependence is highly prevalent and leads to devastating consequences on a personal and societal level. Current treatment approaches are delivered using a fixed-intervention approach. This project aims to develop newer adaptive treatment approaches that "tailor" interventions according to individual patient response. We predict this adaptive approach will optimize outcome and more closely mirror actual clinical practice.

The above stated risks are relatively mild in degree and procedures have been designed to minimize their probability. *We believe this protocol has an extremely favorable risk/benefit ratio.* Our research center has an excellent track record in conducting controlled trials with the utmost attention to safety.

Data and Safety Monitoring Plan

This plan describes the general data and safety monitoring procedures for the proposed study. A detailed DSM plan will be submitted for approval prior to starting the study.

1. The Principal Investigator ([name]) will be responsible for knowing the policies of the local IRB (the UT – Houston Committee for the Protection of Human Subjects, CPHS). The PI will adhere to CPHS policies and maintain accurate documentation of CPHS correspondence and reports (e.g., annual report). The PI will be responsible for documentation and handling of all possible study-related adverse events. The Treatment Research Clinic (TRC) within our Center for Neurobehavioral Research on Addictions (CNRA) has longstanding data collection and safety monitoring systems in place that will be available for the proposed study. These include staff training, manual driven processes, weekly audit of data collection/entry, medical screening with results reviewed by on-site nurse and physician, use of standardized assessments, continued medical monitoring during treatment, use of a certified (CLIA)

analytical laboratory to perform urine toxicology testing, procedures to monitor medication compliance (e.g., riboflavin), collaboration with [name] (Co-I) who oversees data analysis and system management. [name] will assure that the above systems are in place and functioning properly for the duration of the study.

2. A DSM Board will be formed to provide additional, independent oversight of data related to patient safety. Membership will include Drs. [name] (UT-School of Nursing), [name] (Baylor College of Medicine-Psychiatry, [name] (UT-Department of Internal Medicine, Cardiology) and [name] (Baylor College of Medicine). These individuals have served previously on the DSMB for our P50 grant and thus have the relevant expertise and experience in monitoring clinical trials. This committee will perform the following activities: (a) review the research protocol and plans for data and safety monitoring; (b) evaluate study progress, including data quality, participant recruitment rates, retention rates, outcome and adverse experience data, and risk versus benefit profile; (c) make recommendations to terminate the trial because of safety concerns; and (d) protect the confidentiality of the trial data and the results of monitoring.
3. Adverse events (AE) will be reported to the UT-CPHS on an annual basis. Serious adverse events will be reported immediately (verbally within 24 hours) to the UT-CPHS, the DSMB, and to the NIDA. A written report will follow as soon as possible but in no more than three days. The written report will be in the format required by the CPHS and will contain information regarding the date of the AE, description of the AE, severity rating (Grade 1 to 4), assessment of cause, whether the AE indicates an increased risk for current or future subjects, and whether changes to the informed consent form are necessary.

Literature Cited

1. Goldstein, R.Z. and N.D. Volkow, Dysfunction of the prefrontal cortex in addiction: neuroimaging findings and clinical implications. *Nat Rev Neurosci*, 2011. 12(11): p. 652-69.
2. Goldstein, R.Z. and N.D. Volkow, Drug addiction and its underlying neurobiological basis: neuroimaging evidence for the involvement of the frontal cortex. *Am J Psychiatry*, 2002. 159(10): p. 1642-52.
3. Volkow, N.D., J.S. Fowler and G.J. Wang, The addicted human brain: insights from imaging studies. *J Clin Invest*, 2003. 111(10): p. 1444-51.
4. Carroll, K.M., Recent advances in the psychotherapy of addictive disorders. *Curr Psychiatry Rep*, 2005. 7(5): p. 329-36.
5. Carroll, K.M. and L.S. Onken, Behavioral therapies for drug abuse. *Am J Psychiatry*, 2005. 162(8): p. 1452-60.
6. Karila, L., Pharmacological treatments of alcohol and drug addiction: what's new? *Curr Pharm Des*, 2011. 17(14): p. 1320.

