based treatment in the community for patients actively using cocaine. DC educates patients about important concepts in addiction recovery based on the underlying philosophy that physical, emotional, spiritual, and interpersonal needs must all be addressed to support recovery. Accordingly, the DC manual covers the core topics listed in **Table B.3.2.vi**. Masters-level therapists with DC experience from our previous trials^{41, 42} will be trained and supervised by [name] (Co-I).

Contingency Management (CM). We will use the same high-magnitude CM schedule shown previously to be feasible and effective in facilitating initial cocaine abstinence.¹² Subjects will earn vouchers for cocaine-negative urine samples collected at scheduled clinic visits (MWF) each week. Under an escalating reinforcement schedule, voucher values will begin at \$15 and increase by \$10 for each consecutive negative urine. Provision of a cocaine-positive urine or failure to provide a scheduled sample will result in no vouchers earned and will reset the schedule to the initial value (\$15). Bonus vouchers (\$10) will be given for completing all study-related tasks in a given week. Subjects will redeem their earned vouchers for cash loaded to the ClinCard, a reloadable debit card.

Initial response and re-randomization. Following Phase 1 treatment, the primary outcome of response/non-response will be determined. Subjects who submit 6 consecutive (2 weeks) cocaine negative urine samples by week 4 will be classified as responders. Those who fail to meet response criteria will be classified as non-responders.

During second (Phase 2) treatment:

- Responders will continue to receive their assigned initial treatment, as described below.
- Non-responders in each initial treatment arm will be re-randomized to a second treatment consisting of pharmacotherapy augmentation with either modafinil or placebo.

All subjects will attend three clinic visits per week (MWF) during the 8 week second treatment period.

Table B.3.2.vi. 10 Core Topics for ACT and DC

Second (Phase 2) treatments	ACT	DC
Continued ACT or DC. Twice weekly 1-hour ACT and DC sessions will continue during the 8 weeks of second treatment, covering the core topics shown in Table B.3.2.vi.	Preparing to begin	Planning my recovery
	Values	Stages of recovery
	Making contact with the cost of using	People, places, things
	Creative hopelessness	Self-help groups & support systems
	Control v Willingness	Establishing a support system

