Cocaine use outcomes. The primary outcome measure of cocaine use/nonuse will be based on qualitative urine drug screen levels of cocaine metabolite BE, coded as “positive” for cocaine use if BE \geq 150 ng/mL. While this objective measure is considered by some to be the gold standard, we realize that there is no established, “optimal” outcome measure and that urine-based definitions of cocaine use/nonuse have limitations in terms of data loss and carryover effect. Recent procedures for combining self-report and urine BE have been recommended.⁷¹⁻⁷³ As a secondary measure of cocaine use/nonuse, we will apply the SRPHK1 (SelfReportPHarmacoKinetic1) coding method that classifies daily cocaine use/nonuse based on evaluation of self-report using a Timeline Follow-Back (TLFB)⁷⁴ method, quantitative urine BE levels, and the participant’s concordance rate (agreement between self-report and urine result). The SRPHK1 is expected to produce fewer missing data and lower use estimates than urine-based only outcomes.⁷² We will take advantage of available software programs for applying the SRPHK1 conversion.

Safety monitoring. Vital signs assessed at each study visit will include oral temperature, sitting blood pressure, pulse, respiratory rate, and weight. If blood pressure is $> 140/90$, or resting heart rate is above 100bpm, hold medication and consult with study physician, who will make the determination about length of hold, and any additional monitoring or referrals needed prior to continuation. Patients with blood pressure readings with either the systolic or diastolic outside the range of 140/90 or resting heart rate above 100bpm over 3 consecutive visits will be discontinued from the study medication and referred for medical follow-up. There is no protocol for dose reduction with retention in the study, only discontinuation. If other AEs are reported, the study nurse will hold medication and consult with the study physician, who will make the determination about length of hold, and any additional monitoring or referrals needed prior to continuation. Any SAE will result in discontinuation of the study medication and referral for medical or psychiatric follow up. AEs that do not meet these criteria (e.g. severe

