headache) but interfere with the participant's daily activities and are persistent across 3 consecutive visits will also result in discontinuation of study medication and referral for medical or psychiatric follow up. The Systematic Assessment for Treatment and Emergent Events (SAFTEE) will be administered by trained research staff at each study visit to document patient-reported adverse events, serious adverse events, and/or treatment-emergent symptoms. The Concomitant Medications Tracking Log will be used to record any medications taken during the study. The study nurse completing the form will enter the name of the medication, dose/unit, route of administration, date started/stopped, and indication. Reported use of prohibited concomitant medications will be reviewed by the study physician ([name], Co-I) who will make a reasonable judgement about continued participation in the study. Additional measures will be used to monitor treatment-emergent psychiatric symptoms, including the Clinical Global Impression (CGI) scale, a well-established research rating tool for tracking clinical progress over study period and evaluating any change in the severity of psychopathology; and the Beck Depression Inventory-II, a 21-item, self-report rating inventory that measures symptoms of depression. The study physician ([name], Co-I) will be alerted of any psychiatric adverse events or reactions of treatment such as suicidality or worsening of mood symptoms. If clinically indicated in cases of significant worsening or deterioration of patient's functioning, appropriate actions will be taken, including study termination with proper referral. The *Patient-Reported Outcomes Measurement Information System short form (PROMIS-10)* is a global health assessment tool made publically available that allows measurements of general domains of health functioning including overall health, mental health, social health, pain, fatigue, and overall perceived quality of life using a 10-item Likert-type scale (5 = "Excellent/Completely/Never/None" to 1 = "Poor/Not At All/Always/Very Severe").

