exist. Posterior distributions can then be used as informative priors for continued monitoring in expansions of treatments and treatment strategies exhibiting initial promise.

Analytic strategy. Broadly, the analytic strategy will use generalized linear modeling. Continuous, dichotomous and time-to-event data will utilize linear, logistic, and proportional hazards regression respectively. Longitudinal analyses will employ generalized linear mixed models. All of these SAS (ver 9.3) procedures permit Bayesian analyses. Primary analyses will use intention-to-treat principles, with missing observations imputed as positive. Secondary analyses will implement joint modeling of observed outcomes and the missing data which is robust to ignorable missingness.^{81, 82} Sensitivity analyses will evaluate robustness of analytic conclusions to missing data. Non-ignorable missing data patterns will be addressed through pattern-mixture modeling methods.⁸¹ Prior distributions for comparison of proportions will use $\sim \text{Beta}(a = 1, b = 1)$ priors. Linear, logistic and Cox Proportional Hazards regression coefficient priors will take the form $\sim \text{N}(\text{mean} = 0, \text{var} = 1 \times 10^6)$ in the linear, log (odds) and log scales respectively. Level one error variances will be specified as $\sim \text{Inverse Gamma}(\text{shape} = 0.001, \text{scale} = 0.001)$; level two variances will use $\sim \text{Uniform}(0, 1000)$ distributions. Sensitivity analyses using optimistic and pessimistic, skeptical priors will evaluate prior assumptions.^{83, 84} Inverse probability weight will permit unbiased effect size estimates in the context of re-randomization. Finally, coding procedures will permit identification of each salient effect. Specifically, at the initial randomization ACT+CM and DC+CM will be coded as 1 and -1 respectively. For the re-randomization: 1) non-responders receiving continuation therapy will be coded 1 while all other participants will be coded 0; 2) non-responders receiving augmentation will be coded 1 versus 0 for all other participants.

Hypothesis testing.

Hyp. 1. Initial treatment with ACT+CM will produce higher response (abstinence) rates than initial treatment with DC+CM. Logistic regression will evaluate cocaine-abstinence rates at week 4 as a function of treatment assignment.

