Hyp. 1.a. The benefit of ACT+CM over DC+CM on initial response (abstinence) rates will be greater in the subgroup of individuals with higher pretreatment EA scores. Adding the interaction term (EA-by treatment) to the logistic regression model will evaluate the moderating effect of EA.

Hyp. 1.b. ACT+CM effects on initial treatment response will be mediated by the primary hypothesized treatment mechanisms, EA and reward sensitivity. In the context of the direct effect of treatment on response, mediational modeling will evaluate the *indirect* effect of treatment on response via EA and reward sensitivity variables, using the product moment method with bootstrapped 95% CI and Bayesian posterior distributions.

Hyp. 2. For initial non-responders, continued ACT+CM treatment with pharmacotherapy (modafinil) augmentation will be most effective in promoting abstinence relative to treatment combinations involving DC and/or placebo. Logistic regression will evaluate cocaine abstinence at the end of second treatment in a set of contrasts: (1) modafinil versus placebo within each initial treatment; (2) the sequence of ACT+CM with modafinil augmentation versus DC+CM with modafinil augmentation.

Hyp. 3. For initial responders, continued ACT+CM will be more effective (higher abstinence rates; < 46% relapse rate) than continued DC+CM. Logistic regression will evaluate cocaine abstinence/relapse at end of second treatment as a function of initial treatment (ACT+CM vs DC+CM).

Power. Power estimates for Hypotheses 1, 2 and 3 will use as the primary outcome (i.e., “response”), two consecutive weeks of cocaine abstinence (BE ≤ 150 ng/mL). Initial treatment response (abstinence) rates are expected to be $\sim 40\%$, based on our previous study¹² and pooled data across cocaine clinical trials⁸⁵; however we predict a difference in response rates, favoring ACT+CM over DC+CM by about 20%, constituting a clinically meaningful treatment effect. Among initial non responders, we expect at least a

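### Psychiatric worsening may end a patient's study participation, with no urine collection provided afterwards, so such a patient can be scored non-abstinent in Hyp. 2 whatever they used

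*Combined protocol and SAP*

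**What the plan says.** The psychiatric rule appears three times: under Assessment Schedule (Safety monitoring), Potential Risks (Medication) and Protection Against Risk. It reads "If clinically indicated in cases of significant worsening or deterioration of patient's functioning, appropriate actions will be taken", and study termination is the action named: "appropriate actions will be taken, including study termination with proper referral". The neighbouring rules are worded differently. A patient with out-of-range blood pressure or heart rate at three consecutive visits "will be discontinued from the study medication and referred for medical follow-up"; the rules for serious adverse events and for persistent adverse events likewise speak of stopping study medication.

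On follow-up, the Study Design section states "All subjects will attend three clinic visits per week (MWF) during the 8 week second treatment period". No section says what happens to urine collection once a patient has been terminated. The single safety visit 7 to 10 days after treatment covers side effects and psychiatric symptoms and mentions no urine sample.

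On scoring, the Analytic strategy says "Primary analyses will use intention-to-treat principles, with missing observations imputed as positive". For Hyp. 2, "Logistic regression will evaluate cocaine abstinence at the end of second treatment in a set of contrasts". The Power section takes two consecutive weeks of abstinence as the outcome for Hyp. 1 to 3.

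**The concern.** Taken together, these rules turn a clinical decision about safety into an abstinence outcome. A non-responder who is re-randomised, deteriorates and is terminated in Phase 2 before meeting the criterion is a treatment failure by rule, even if cocaine-free. Hyp. 2 is where this matters most. It compares modafinil with placebo in small cells, and the Potential Risks section lists psychiatric reactions as a recognised risk of modafinil, so the loss could differ between arms. The benchmark is the plan's own: a probability of benefit above 0.80 is stated to be enough for a Go decision.

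The missing-equals-positive convention is declared, and the planning effect sizes share it; it is not in question here. The question is whether the protocol forgoes urines that could have been collected.

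**Working it through.** **Plan's own figure.** Table B.3.2.x gives power 0.81 for contrasts 5 vs 6 and 7 vs 8, which are taken here as modafinil against placebo, at posterior threshold 0.80 with average effects 0.17 and 0.13. The cell rates and cell sizes are in a figure not available here, so 0.81 cannot be reproduced. Nothing below depends on it.

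**Cell sizes (assumed).** N = 160 gives 80 per initial arm if split equally. Non-responders per cell = 80 × (1 − response)/2. The Power section expects about 40% response and a 20-point advantage for ACT+CM, so two readings are used:
- DC 40%, ACT 60%: 80 × 0.60/2 = 24 and 80 × 0.40/2 = 16.
- DC 30%, ACT 50%: 80 × 0.70/2 = 28 and 80 × 0.50/2 = 20.

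**One patient.** 1/28 = 3.6 points; 1/16 = 6.25, or 6.3 points.

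**Effect on the posterior.** The plan says "Linear, logistic and Cox Proportional Hazards regression coefficient priors will take the form" of a normal distribution with mean 0 and variance 10⁶. That is effectively flat on the log-odds scale, so with y abstinent of n the cell posterior is Beta(y, n − y). Pr(modafinil rate > placebo rate), by numerical integration, with one fewer modafinil abstainer in the last column:

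| n per cell | modafinil vs placebo abstainers | Pr | Pr, one fewer on modafinil |
|---|---|---|---|
| 16 | 6 vs 3 | 0.893 | 0.805 |
| 16 | 8 vs 5 | 0.868 | 0.775 |
| 20 | 7 vs 4 | 0.865 | 0.776 |
| 24 | 9 vs 5 | 0.905 | 0.843 |
| 24 | 8 vs 5 | 0.843 | 0.755 |
| 28 | 10 vs 6 | 0.888 | 0.824 |

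Three of the six rows cross 0.80 and three do not.

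**How often one patient decides.** All binomial results were enumerated for n = 16, 20, 24 and 28, an assumed placebo rate of 0.20 or 0.30, and effects of 0.13 and 0.17. The probability that a result lies above 0.80 and would lose that with one fewer modafinil abstainer is 9.1% to 13.9%. As a share of the results above 0.80, it is 13% to 27%.

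**Effect of a termination rate t (assumed).** Terminated patients are scored non-abstinent, so the observed rate is p × (1 − t). Over the same grid:
- t = 2% on modafinil only: the chance of exceeding 0.80 falls by 1.4 to 2.5 points.
- t = 5% on modafinil only: it falls by 3.6 to 6.2 points. For example, at n = 24 with 0.30 vs 0.43 it goes from 0.577 to 0.514 (6.2 points before rounding). Expected abstainers lost per cell = n × 0.05 × p, from 16 × 0.05 × 0.33 = 0.26 to 28 × 0.05 × 0.47 = 0.66.
- t = 5% in both arms: it falls by 0.6 to 2.1 points.
- t = 0: no effect.

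**Why these are upper bounds on the gain.** The formula assumes that terminated patients would have been abstinent at the full rate of their arm, and that every such patient could still give six consecutive negative urines. Neither is likely after a deterioration serious enough to end participation.

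**The case against.** - **Termination is discretionary.** The physician can already stop the capsules and keep the patient in the study. This stands; the text permits the loss and does not require it.
- **Few outcomes are recoverable.** A patient must be unwell enough to be terminated, yet attend six visits in a row and test negative at each. This stands, and it is why the gain is called partial.
- **The contrast with the medication-only rules is not clean.** The Safety monitoring text also says that there is no provision for reducing the dose while staying in the study, only for discontinuation. A reader might infer that patients stopped under the blood-pressure or adverse-event rules are certainly followed to week 12; the documents do not say so. The fix should therefore cover those exits too.
- **Counting a patient removed for deterioration as a failure is a legitimate composite outcome.** It is, and the plan's effect sizes use the same convention. But the plan defines the outcome by urine results and does not name withdrawal for safety as a component of failure.
- **Other safeguards exist.** Joint and pattern-mixture models are planned, the safety board reviews retention, and a detailed monitoring plan that is not in these documents may add procedures. The models still have to work without urines that could have been collected, and nothing available here supplies those urines.
- **The Phase 2 window is open.** In Phase 1, "Subjects who submit 6 consecutive (2 weeks) cocaine negative urine samples by week 4 will be classified as responders". If an earlier run of six also counts in Phase 2, a patient terminated after such a run is unaffected. This stands.

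**Conclusion.** The gap is real, and closing it is an optional, inexpensive improvement. A Phase 2 patient terminated before meeting the criterion is non-abstinent in Hyp. 2 by rule. The size depends on a termination rate that the documents do not give: nothing at zero, about 1.4 to 2.5 points off the chance of exceeding 0.80 at 2% on modafinil only, and 3.6 to 6.2 points at 5%. These figures rest on assumed cells of 16 to 28, placebo rates of 20% to 30%, and the plan's effects of 13 and 17 points.

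A reader might infer that Hyp. 2 is biased against modafinil. The documents do not support that. They name psychiatric reactions as a risk but give no frequency, describe the drug's adverse experiences as mild to moderate, exclude patients with unstable psychiatric disorders, and apply the same rule to placebo patients. Nor does this show that the stated power of 0.81 is wrong, or that scoring missing urines as positive is wrong. Hyp. 2 is listed as a secondary aim.

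**What to change.** In the three places where the psychiatric rule appears, replace termination from the study with *ending study treatment, with referral*. Then state once that any patient whose medication or treatment is stopped for safety is offered urine collection at the scheduled Monday, Wednesday and Friday visits to week 12, unless consent is withdrawn or the physician judges attendance unsafe. This should include stops under the blood-pressure and heart-rate, serious-event, persistent-event and prohibited-medication rules. Score the urines obtained as observed, keep missing as positive in the primary analysis, and report physician-ordered exits by arm. The physician's authority to stop treatment is unchanged.

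The cost is up to three visits a week for a few off-treatment patients, a definition of what a reduced visit contains (several safety scales are otherwise due at every visit), a small consent-form edit, and one line in a results table.
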